There is a small risk of topical reaction to the EMLA cream. If irritation does occur, the area of irritation will be cleansed with water and the procedure will be postponed until the irritation is resolved. The subjects will return to clinic to assess for resolution of the area and their indicated vulvar biopsy.

Costs to the Subject

No additional costs will be incurred by the participant as a result of participating in this study

Data Analysis and Statistical Considerations

A 16-mm difference on a standard 100-mm visual analog pain scale was deemed clinically significant. In order to detect a 16-mm difference with 90% power at an alpha level of 0.05 assuming a standard deviation of 25-mm, we estimated a needed sample size of 53 participants in each treatment arm. However, due to time limitations, data collection will end on March 12, 2019. Only patients consented on or prior to March 12, 2019 will be included in the study. Data will be recorded using Research Electronic Data Capture (REDCap), and the database will be locked on March 13, 2019. Pain will be measured during the application of EMLA cream or lidocaine injection, and immediately after biopsy. The primary outcome will be the highest pain score recorded during the procedure. The primary outcome sinclude pain score at vulvar biopsy, patient tolerability and acceptability, and provider's satisfaction with the procedure. All testing will be performed at a two-tailed significance level of 0.05.

If significance for the primary objective is not achieved, then patient accrual will continue based on a new sample size determined by the primary results of this analysis. This will be the number of new patients that need to be enrolled. Outcomes will be assessed again at the point when the final sample size is achieved.

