#### Exposure

• Patients were randomly assigned with equal probability to receive either EMLA cream or a lidocaine injection for analgesia for vulvar biopsy

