**Analysis:** Using the difference in means between groups and the estimate of the standard deviation, the sample size needed to detect the observed difference in pain scores between the two treatment arms at 90% power with an alpha level of 0.05 using a two-sample t-test will be calculated. This will be the number of patients that will need to be NEWLY accrued. The current patients do not count towards this sample size.

**Conclusions:** Since the highest pain score was significantly lower in the EMLA cream group compared to the lidocaine group, the trial does not need to continue.

4. Objective: Compare secondary and exploratory outcomes between treatment arms

**Analysis:** The secondary objective, pain at vulvar biopsy, will be compared between treatment arms using linear regression, controlling for baseline pain, similar to the primary objective. The exploratory objectives, excluding provider's response to "overall, how satisfied were you with the procedure," will be compared between treatment arms using Wilcoxon rank sum test. A significant p value would mean that one of the treatment arms tended to have higher scores on the VAS than the other. Since the same providers are rating their satisfaction with the procedure multiple times, the responses will be correlated. To take this into account, provider procedure satisfaction scores will be compared between treatment arms using generalized estimating equations (GEE) assuming a normal distribution. The working correlation matrix will be chosen using QIC and the robust variance estimator will be used.

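### The protocol states 90% power for a 16-mm difference but gives no power for the calendar-truncated sample, which at 37 patients was about 47%; the consent-date sentence also needs reconciling with the extension paragraph

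*Protocol*

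**What the plan says.** **Size and power.** In the Protocol, Data Analysis and Statistical Considerations, the calculation is set up as "In order to detect a 16-mm difference with 90% power at an alpha level of 0.05", "assuming a standard deviation of 25-mm", and ends with "we estimated a needed sample size of 53 participants in each treatment arm". The Research Abstract repeats the 16 mm, the 90% and the 0.05, but gives 53 as a total and states no SD.

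**Calendar stop.** The same statistical section then says that time limitations end data collection on March 12, 2019, adds "Only patients consented on or prior to March 12, 2019 will be included in the study", and locks the database the next day. It gives no power or detectable difference for the sample that results. The abstract does not mention the stop.

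**Extension.** The next paragraph provides that, if the primary objective is not significant, "then patient accrual will continue based on a new sample size determined by the primary results of this analysis", with a second assessment at the final size. SAP Analysis Objectives, objective 3, calls the March 2019 analysis interim. Of the recalculated size it says "This will be the number of patients that will need to be NEWLY accrued", and it does not count current patients towards that number.

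**What happened.** SAP objective 1 reports 37 patients, 19 and 18. Objective 2 reports a significant primary result, and objective 3 concludes that the trial need not continue.

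**The concern.** A reader who wants to know what the trial could detect finds one power statement for the 16-mm design difference, and it belongs to 106 patients. The sample analysed is 37/106 = 35% of that. The protocol says that the planned size gives way to the calendar, but leaves the reader to work out the consequence. The abstract does not even give the warning. The SAP's caution about the trial not being powered is attached only to the secondary and exploratory outcomes.

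At stake is how the primary result is read. Someone who takes the design to have had 90% power for 16 mm will expect more precision than 37 patients give. A non-significant result, which the protocol's own hypothesis predicted, would have been easy to over-read as evidence of no difference.

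The consent-date sentence is a second, smaller matter. It defines who is in the study as a whole. Anyone accrued after an analysis of data locked on March 13 must consent after March 12. Taken alone, the sentence shuts out exactly the patients whom the next paragraph would recruit, on the branch that the protocol hypothesised.

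**Working it through.** **Inputs.** From the Protocol statistical section: difference 16 mm, SD 25 mm, power 90%, and "All testing will be performed at a two-tailed significance level of 0.05". From SAP, Exposure: "Patients were randomly assigned with equal probability to receive either EMLA cream or a lidocaine injection", so 1:1 allocation. From SAP objective 1: 19 and 18 patients. From SAP Table 2.1: highest pain score, mean (SD), 26.7 (29.0) mm for EMLA and 52.5 (32.0) mm for lidocaine.

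**1. Reproduce the plan's figure.**
- Normal approximation: n per arm = 2 × (1.960 + 1.282)² × (SD/difference)² = 2 × 10.507 × (25/16)² = 51.3, rounded up to 52.
- Two-sample t-test: 52.3, rounded up to 53. The protocol's 53 per arm is correct.
- Power at 53 per arm: noncentrality 16 / (25 × √(2/53)) = 3.29 on 104 degrees of freedom, giving 90.4%.

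**2. Power for the sample that the stop delivered.**
- Standard error = 25 × √(1/19 + 1/18) = 25 × 0.3289 = 8.22 mm.
- Noncentrality = 16/8.22 = 1.95 on 35 degrees of freedom; two-sided critical value 2.03.
- Power = 47.3% (noncentral t). The normal approximation gives 49.4%.

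**3. Difference detectable with 90% power at 19 and 18, SD 25.**
- Normal approximation: (1.960 + 1.282) × 8.22 = 26.7 mm.
- Noncentral t: 27.4 mm.

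**4. Sensitivity to the SD.** The pooled observed SD is √[(18 × 29.0² + 17 × 32.0²)/35] = 30.5 mm. Power for 16 mm at 19 and 18 is then 34.2%. This uses trial data and was not available at planning; it shows direction only.

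**5. Is the extension a route back to 53 per arm?** SAP objective 3 sizes it from the observed difference and SD, counting new patients only. With the observed estimates (difference 52.5 − 26.7 = 25.8 mm, SD 30.5 mm), the normal approximation gives 2 × 10.507 × (30.5/25.8)² = 29.4, rounded up to 30 per arm; the t-test gives 30.4, rounded up to 31. This is only an illustration, because at that difference the extension did not trigger, and a smaller observed difference would give a larger number. Either way, the size follows from the interim estimates and is not a top-up to 53 per arm.

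**6. The two rules side by side.** The consent sentence limits the study to patients consented by March 12, 2019. The following paragraph continues accrual on the basis of the results of this analysis and assesses outcomes again. The SAP speaks of an interim analysis and separates current from newly accrued patients. The later passages make sense only if the date fixes the first data cut. The protocol sentence does not say so.

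**The case against.** **The protocol is open about the shortfall.** It calls 53 per arm the number needed and says at once that time limits end collection earlier. That stands: a reader might infer that the protocol claims 90% power for the 37 patients, and it does not. Nor is the design calculation the only power figure, since SAP objective 3 also specifies 90% for the recalculated size. What remains is that the reduced power is nowhere quantified and that the abstract omits the stop.

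**The extension patients were never meant to be barred.** A reader might infer from the consent sentence that a second assessment would contain no eligible new patient. The next paragraph and the SAP's interim label do not support that; they describe a staged plan. The objection stands to the extent that this is loose wording to reconcile.

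**The consent wording did not cause the shortfall.** This also stands. The calendar stop did, and admitting later patients would not by itself deliver 53 per arm, because the extension is a separately sized cohort.

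**There was no practical effect.** The extension was conditional and not triggered, and the documents show nobody excluded by the wording. This limits the importance of the wording conflict, but not of the power statement.

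**Retrospective power adds little once a confidence interval exists.** This is fair for the figure based on the observed SD. The 47% and 27 mm use only the protocol's own difference and SD with the enrolled numbers, so they restate the design. The reported interval (−45.1 to −6.3 mm, half-width (45.1 − 6.3)/2 = 19.4 mm) is the better guide to precision. It tells the same story, because the half-width exceeds 16 mm.

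**Conclusion.** The concern holds in a limited form. The 53-per-arm calculation is right, but the calendar stop delivered 37 patients. For them, power to detect 16 mm is about 47% against the stated 90%, and the difference detectable with 90% power is about 27 mm against 16 mm. These figures assume SD 25 mm in both arms, a two-sided t-test at 0.05 and complete data on 19 and 18 patients. The SAP's primary model adjusts for baseline pain. Its reported half-width of 19.4 mm is close to that of an unadjusted comparison at the observed SD (2.03 × 30.5 × 0.3289 = 20.4 mm), so adjustment changes little here.

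The consent-date sentence and the extension paragraph contradict each other literally and should be reconciled. The documents do not support going further: no patient is shown to have been lost, and the wording did not produce the shortfall. Low power for 16 mm does not by itself overturn the reported difference of 25.7 mm.

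**What to change.** 1. **Power.** In the Protocol's statistical section, beside the 53-per-arm figure, add: the calendar stop on March 12, 2019 yielded 37 patients (19 and 18), for which power to detect 16 mm at SD 25 mm is about 47% (two-sided t-test, alpha 0.05), with about 27 mm detectable at 90% power. The protocol version supplied carries an approval date of September 23, 2019, after the lock, so the enrolled number was available.
2. **Abstract.** Put the same statement in the Research Abstract and mention the stop. While that sentence is open, align its total of 53 with the 53 per arm of the statistical section; 53 in total would give only about 63% power for 16 mm at SD 25 (t-test, 26 and 27 per arm).
3. **Consent window.** Reword the sentence so that patients consented by March 12, 2019 are included in the first (interim) analysis, and patients consented later form the extension cohort only if the extension is triggered.

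**Cost.** A few sentences and a less favourable stated power. No extra patients and no reanalysis are needed.

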# Table 1.1. Patient demographics and characteristics

2. Objective: Compare highest subjective pain score between patients receiving EMLA cream vs. lidocaine

**Analysis:** Linear regression will be used to test if the highest pain score differs between treatment arms, controlling for baseline pain. The regression coefficient, 95% confidence interval, and p value will be reported for the treatment effect. A significant p value would indicate that the highest pain score, on average, differed between the two treatment arms. If there is not a significant difference between treatment arms with regards to the highest pain score, then the mean and variance estimates from these patients will be used to recalculate the sample size needed (objective 3).

**Conclusions:** The highest pain score was created as the maximum between pain during application of anesthesia and pain immediately following biopsy. The median highest pain score in the EMLA cream group was 20.0 mm vs. 56.5 mm in the lidocaine injection group.

Table 2.1. Highest pain score by treatment arm					
	EMLA cream (N=19)	Lidocaine injection only (N=18)	Total (N=37)		
Highest pain score (n	nm)				
Ν	19	18	37		
Mean (SD)	26.7 (29.0)	52.5 (32.0)	39.2 (32.8)		
Median	20.0	56.5	27.0		
Q1, Q3	5.0, 50.0	26.0, 80.0	12.0, 61.0		
Range	(0.0-100.0)	(5.0-100.0)	(0.0-100.0)		

All patients in the lidocaine injection group reported having the same as or more pain during the injection than the biopsy. Four out of nineteen patients in the EMLA cream group reported more pain from the application of the cream than the biopsy, and three reported the same amount of pain.

Frequency Row Percent	More pain from biopsy	Same amount of pain	More pain from application of anesthesia	Total
Lidocaine injection only	0 0.00	1 5.56	17 94.44	18
EMLA cream	12 63.16	3 15.79	4 21.05	19
Total	12	4	21	37

From the linear regression model, patients that received EMLA cream were expected to report their highest pain score 25.7 mm lower than the lidocaine injection group (95% CI = [-45.1, -6.3], p < 0.01). In other words, the highest pain score in the EMLA cream group was significantly lower than in the lidocaine injection group.

**3. Objective:** Calculate the new sample size needed using effect estimates from the interim analysis

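### The stop-or-extend rule tests the primary outcome twice at an unadjusted two-sided 0.05, so its overall type I error as written is about 10%

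*Protocol*

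**What the plan says.** The protocol's Data Analysis and Statistical Considerations section gives one level for everything: "All testing will be performed at a two-tailed significance level of 0.05". It sets aside the target of 53 per arm ("However, due to time limitations, data collection will end on March 12, 2019") and then gives the rule: "If significance for the primary objective is not achieved, then patient accrual will continue based on a new sample size". Of the new sample size it says "This will be the number of new patients that need to be enrolled", and it closes with "Outcomes will be assessed again at the point when the final sample size is achieved".

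The SAP repeats the rule under Analysis Objectives. Objective 2 tests highest pain score by linear regression adjusted for baseline pain, and a non-significant result leads to Objective 3: "Calculate the new sample size needed using effect estimates from the interim analysis". The extension is sized for the observed difference "at 90% power with an alpha level of 0.05 using a two-sample t-test will be calculated", and the current patients do not count towards it.

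The Objective 2 conclusion reports that the EMLA group's highest pain score was expected to be "25.7 mm lower than the lidocaine injection group (95% CI = [-45.1, -6.3], p < 0.01". The Objective 3 conclusion is that, because of this significant result, the trial can stop.

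Neither document gives an alpha split, a stopping boundary, a combination test or a maximum extension. Both say that the new sample size consists of new patients, but neither says whether the first 37 enter the second test.

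**The concern.** A rule that stops on success at 0.05, and otherwise recruits further and tests again at 0.05, gives the treatment comparison two chances to be declared significant. Its false-positive rate is that of the whole rule and exceeds that of either test. A reader who sees 0.05 as the only level will assume a 5% procedure.

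Two further things depend on this. The reported p value needs to be read against the level that a two-look rule would require. The estimate also comes from a trial that ended because the first look was significant, and this selection tends to make it too large.

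**Working it through.** **Inputs.** Two-sided 0.05 for each test, and a planned difference of 16 mm with SD 25 mm, 90% power and 53 per arm (protocol, Data Analysis and Statistical Considerations). First look of 19 and 18 patients, estimate -25.7 mm, 95% CI -45.1 to -6.3 mm, and the rule for sizing the extension (SAP, Objectives 1 to 3).

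**1. The plan's own figure.** n per arm = 2(1.960 + 1.282)² × 25²/16² = 2 × 10.507 × 2.441 = 51.3, so 52 by the normal formula. The two-sample t version gives 52.29, rounded up to 53 per arm. The stated figure reproduces.

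**2. Second test on new patients only.** The two tests are independent when there is no true difference:

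1 - 0.95² = 0.05 + 0.95 × 0.05 = 0.0975.

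**3. Second test pooled with the first 37.** Let z be the first-look statistic. Sizing for the observed difference and SD gives n2/n1 = r = 10.507/z². The pooled statistic is (z + √r × Z2)/√(1 + r), where Z2 comes from the new patients. Total error is

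0.05 + the integral, over |z| < 1.96, of φ(z) × P(|pooled statistic| > 1.96 given z) = 0.1019.

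A simulation with t-tests (2,000,000 trials with no true difference, 19 and 18 at the first look) gave 9.72% for new patients only and 10.17% for pooling. Pooling is slightly worse because a near miss at the first look leads to a small extension, so the favourable first-look result keeps more weight.

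**4. How far the missing cap matters.** With no true difference, triggered extensions have a median of about 470 per arm (quartiles about 168 and 2,100). Some might not be completed. The documents do not address this, so what follows is illustrative:

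| Assumed limit per arm | What happens above it | New only | Pooled |
|---|---|---|---|
| none | every extension completed | 9.75% | 10.2% |
| 500 | abandoned, no second test | 7.4% | 7.9% |
| 200 | abandoned, no second test | 6.4% | 6.9% |
| 500 | run at the limit and tested | 9.75% | 10.1% |
| 200 | run at the limit and tested | 9.75% | 9.8% |

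Abandonment brings the error down towards 5%. A cap alone does not.

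**5. The first-look p value implied by the reported interval.** The half-width is (45.1 - 6.3)/2 = 19.4 mm. With 37 patients and three coefficients there are 34 degrees of freedom.

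- t distribution: SE = 19.4/2.032 = 9.55, t = 25.7/9.55 = 2.69, p = 0.011 (0.0106 to 0.0113 over rounding of the reported figures).
- Normal quantile: SE = 19.4/1.96 = 9.90, z = 2.60, p = 0.009.

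The t-based value does not agree with the reported p < 0.01. The normal-based value does.

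**6. Levels that would hold 5% overall with every extension completed.**

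- New patients only: 1 - √0.95 = 0.0253 at each look.
- Simple pooling: about 0.023 at each look (0.0232 to 0.0234, depending on the level used for sizing). Using 0.0253 here would leave about 5.4%.
- Equal-weight inverse-normal combination: |z| > 2.178, which is 0.0294 at each look.

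Both implied p values are below all three.

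**7. Interval at the adjusted level.** At 0.0253 with 34 df the quantile is 2.34, so the half-width is 2.34 × 9.55 = 22.3 mm and the interval is about -48.0 to -3.4 mm.

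**The case against.** The strongest reply is that the second test never took place. The first look on its own had a 5% error, it was significant, and the implied p value meets every equal-split level in the working. What remains concerns a branch that was not used. The documents also never claim 5% control across both looks. This stands, and it limits the consequence. It does not remove the point, because the error rate belongs to the rule under which success was declared, and the SAP applied that rule when it stopped the trial.

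It could also be said that an extension made up of new patients is a separate trial. That is the new-patients-only reading, and the chance that the rule produces at least one false positive is still 9.75%. The protocol's reference to a final sample size does not rule out pooling either.

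An error rate below 10% can be argued if unrealistically large extensions would have been dropped. That is reasonable, but the caps and the abandonment are assumptions from outside the documents, so the figures in step 4 are not bounds.

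A reader might go further and infer that the significant result is invalid, or that it fails a proper interim boundary. The documents do not support this. A very strict early boundary presupposes a planned fraction of the total information, and an uncapped extension sized from the observed data has no such fraction.

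**Conclusion.** The point holds as a flaw in the rule's error control. Followed as written, the rule has an overall type I error of about 10%: 9.75% with new patients only and 10.2% with pooling, against the single stated level of 0.05. Both figures assume that every triggered extension is completed. If some were abandoned, the error would lie between 5% and 10%.

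The extension was not triggered, so this does not by itself overturn the first-look finding. It would be wrong to infer that the trial made two tests, or that the documents assert an overall 5%: only one test was run, and 0.05 is simply the only level they give. The 25.7 mm estimate does need a caution, because the trial stopped on first-look significance. The disagreement between the interval and p < 0.01 may come only from the choice of distribution, but it has to be settled by the exact value. This should be fixed, at low cost.

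**What to change.** In the SAP conclusions and the results report, and in the protocol if the rule is kept:

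- State that the 37-patient analysis was the first look of a two-look rule, with each look at an unadjusted 0.05 and an overall error of up to about 10%. Do not describe the trial as having an overall alpha of 0.05.
- Report the exact p value from the baseline-adjusted model and the distribution used.
- As a sensitivity check labelled post hoc, compare that p value with 0.0253 (second test on new patients only), about 0.023 (simple pooling) and 0.0294 (equal-weight inverse-normal combination).
- Add one sentence saying that the 25.7 mm estimate comes from a trial stopped on first-look significance and so tends to be too large.

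Any future use of the rule should fix in advance the alpha split, the maximum extension and whether first-stage patients enter the second test.

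The cost is wording and one p value, with no new data. The downside is a smaller stated margin of significance, with an interval of about -48.0 to -3.4 mm at the 0.0253 level. The post hoc comparison informs the reader but does not give the trial the error control that the rule lacked.

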#### **Project Summary**

The current standard at the Duke Cancer Center Gynecology Oncology Clinic is to use a lidocaine injection as local anesthesia prior to vulvar biopsy. The injection itself is not without pain and awaiting the injection frequently induces anxiety in patients. Other studies have examined the use of a topical anesthetic in addition to or in place of injected anesthesia. A previous study has found that EMLA cream is associated with less pain at the time of anesthesia administration, but injection anesthesia resulted in better biopsy pain control. Pain was measured on a 100 mm visual analog scale at the time of anesthesia administration and immediately following biopsy. The purpose of this study is to compare EMLA cream to lidocaine injection for analgesia for vulvar biopsy using the highest recorded pain score during the procedure.

